9.4 STATISTICAL ANALYSES

9.4.1 GENERAL APPROACH

Continuous variables will be summarized using descriptive statistics such as mean, standard deviation, median, minimum, and maximum. Categorical variables will be summarized by count and proportion.

9.4.2 ANALYSIS OF THE PRIMARY EFFICACY ENDPOINT(S)

Phase I:

There are no primary efficacy endpoints for Phase I. The recommended Phase II dose is defined as the highest dose level for which at most 1 out of 6 patients experience a DLT.

Phase II:

The primary efficacy endpoint is ORR. ORR is defined as the proportion of patients with RECIST disease response (CR, PR). All patients that do not meet the criteria for an objective response by the analysis cutoff date will be considered non-responders.

Phase II is utilizing an optimal Simon's two-stage design. As such, 14 patients will be enrolled in the first stage. If 5 or fewer patients respond (CR or PR), the study will be terminated due to futility. Otherwise, an additional 30 patients will be enrolled in the second stage. As per the decision rules of the design, the null hypothesis will be rejected if at least 21 patients respond (CR or PR) out of the 44 total patients. The ORR and 95% exact confidence interval will be reported.

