9 STATISTICAL CONSIDERATIONS

9.1 STATISTICAL HYPOTHESES

- Primary Efficacy Endpoint(s):

Phase 1:

The primary objectives are to assess safety and determine the recommended Phase II dose cabozantinib in combination with the standard of care, pembrolizumab. There are no primary efficacy endpoints for Phase I.

Phase 2:

The primary objective is to determine whether treatment with combination cabozantinib and pembrolizumab will increase the objective response rate (ORR) in patients with advanced melanoma compared to historic estimates for patients treated with pembrolizumab monotherapy. Historic ORR in patients treated with pembrolizumab monotherapy is reported to be approximately 35% [N Engl J Med. 2015 Jun 25;372(26):2521-32]. We anticipate the addition of cabozantinib will increase the ORR to 55%. In statistical terms, we are testing the null hypothesis $H_0: \text{ORR} \leq 35\%$ versus the alternative hypothesis $H_1: \text{ORR} \geq 55\%$.

- Secondary Efficacy Endpoint(s):

There are no formal and testable hypotheses for secondary endpoints.

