9.2 SAMPLE SIZE DETERMINATION

Phase 1:

Phase I will utilize a standard 3+3 dose escalation design. A minimum of 6 and a maximum of 18 evaluable patients are required.

Phase 2:

When testing the null hypothesis that the $\text{ORR} \leq 35\%$ versus the alternative hypothesis that the $\text{ORR} \geq 55\%$, a sample size of 44 evaluable patients will ensure 80% power to detect a 20% absolute increase in ORR using an optimal Simon's two-stage design (Simon, 1989). Power estimates are based on an alpha = 0.05.

Based on historical trends our institution, the anticipated accrual rate is 2-3 patients per month.

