9.3 POPULATIONS FOR ANALYSES

The safety population will include all enrolled patients who receive at least 1 dose of both cabozantinib and pembrolizumab. The safety population will be the analysis population for the safety analyses.

The modified intention-to-treat (mITT) population will comprise all patients who receive at least 1 dose of both pembrolizumab and cabozantinib, and who have baseline and at least 1 post-baseline imaging assessment. The mITT is the analysis population for the efficacy analysis.

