- All of the patients who met the eligibility criteria should be included in the main analysis of the response rate. Patients in response categories 4-9 should be considered as failing to respond to treatment (disease progression). Thus, an incorrect treatment schedule or drug administration does not result in exclusion from the analysis of the response rate. Precise definitions for categories 4-9 will be protocol specific.
- All conclusions should be based on all eligible patients.
- Subanalyses may then be performed on the basis of a subset of patients, excluding those for whom major protocol deviations have been identified (e.g., early death due to other reasons, early discontinuation of treatment, major protocol violations, etc.). However, these subanalyses may not serve as the basis for drawing conclusions concerning treatment efficacy, and the reasons for excluding patients from the analysis should be clearly reported.
- The 95% confidence intervals should be provided.

Protocol Appendix B- Performance Status Criteria

ECOG Performance Status Scale		Karnofsky Performance Scale	
Grade	Descriptions	Percent	Description
0	Normal activity. Fully active, able to carry on all pre-disease performance without restriction.	100	Normal, no complaints, no evidence of disease.
		90	Able to carry on normal activity; minor signs or symptoms of disease.
1	Symptoms, but ambulatory. Restricted in physically strenuous activity, but ambulatory and able to carry out work of a light or sedentary nature (e.g., light housework, office work).	80	Normal activity with effort; some signs or symptoms of disease.
		70	Cares for self, unable to carry on normal activity or to do active work.
2	In bed <50% of the time. Ambulatory and capable of all self-care, but unable to carry out any work activities. Up and about more than 50% of waking hours.	60	Requires occasional assistance, but is able to care for most of his/her needs.
		50	Requires considerable assistance and frequent medical care.
3	In bed >50% of the time. Capable of only limited self-care, confined to bed or chair more than 50% of waking hours.	40	Disabled, requires special care and assistance.
		30	Severely disabled, hospitalization indicated. Death not imminent.
4	100% bedridden. Completely disabled. Cannot carry on any self-care. Totally confined to bed or chair.	20	Very sick, hospitalization indicated. Death not imminent.
		10	Moribund, fatal processes progressing rapidly.
5	Dead.	0	Dead.

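### Does a 95% exact interval for ORR conflict with a decision rule that is a one-sided 5% test?

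*Combined protocol and SAP*

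**What the plan says.** Section 9.1 sets directional hypotheses for phase 2: an ORR of at most 35% under the null, taken from historical pembrolizumab monotherapy, against at least 55% with the combination.

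Section 9.2 names an optimal Simon two-stage design and states that "a sample size of 44 evaluable patients will ensure 80% power to detect a 20% absolute increase in ORR". On the error rate it says only "Power estimates are based on an alpha = 0.05", with no mention of sidedness.

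Section 9.4.2 gives the rule. Fourteen patients enter stage 1, and the trial stops for futility at 5 or fewer responders. Otherwise 30 more are enrolled, and "the null hypothesis will be rejected if at least 21 patients respond (CR or PR) out of the 44 total patients". The next sentence is the only one about precision: "The ORR and 95% exact confidence interval will be reported". The exact method is not named.

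Two other places bear on the interval. Section 9.4.3 plans the same kind of 95% exact interval for DCR, and Protocol Appendix A says "The 95% confidence intervals should be provided". Nowhere do the documents give the interval a part in the decision, and nowhere do they say how it relates to the test.

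**The concern.** In a single-arm trial judged against a fixed 35%, many readers will check whether the interval excludes 35%. If the test spends 5% in one tail and the interval 2.5%, some counts will reject the null while the reported interval still contains it. The headline would then say that ORR exceeds 35% beside a single interval that includes 35%, with no explanation in the plan.

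A reader who judged success by the interval would in effect ask for more responders than the design does. A team that picked a friendlier interval after seeing such a count would look post hoc. Because section 9.2 does not say one-sided, someone might also wonder whether the test was meant to match a two-sided 95% interval.

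**Working it through.** **Inputs.** Null 0.35 and alternative 0.55 (9.1); alpha 0.05 and 80% power (9.2); n1 = 14, stop at 5 or fewer, n2 = 30, reject at 21 or more of 44 (9.4.2). The 95% exact interval is read as two-sided Clopper-Pearson (an assumption, since the method is not named). Exactly 44 patients are assumed to be analysed.

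**Step 1: reproduce the design.** The probability of passing stage 1 and ending with at least r responders is

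R(r, p) = sum over x = 6 to 14 of P(X1 = x) × P(X2 ≥ r − x), with X1 ~ Bin(14, p) and X2 ~ Bin(30, p).

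- R(21, 0.35) = 0.0458, the type I error.
- R(21, 0.55) = 0.8001, the power.

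A grid search at one-sided alpha 0.05 and 80% power returns this same design as optimal, with expected size under the null 14 + 30 × (1 − 0.6405) = 24.8. The plan's figures are right. Since 0.0458 is above 0.025, the rule can only be a one-sided 5% test.

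**Step 2: the planned interval.** For s responders of 44, the lower limit is the 0.025 quantile of Beta(s, 45 − s) and the upper limit is the 0.975 quantile of Beta(s + 1, 44 − s).

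| Responders | Raw ORR | 95% exact interval | Contains 35%? | Rejects null? |
|---|---|---|---|---|
| 20 | 45.5% | 30.4% to 61.2% | yes | no |
| 21 | 47.7% | 32.5% to 63.3% | yes | yes |
| 22 | 50.0% | 34.6% to 65.4% | yes | yes |
| 23 | 52.3% | 36.7% to 67.5% | no | yes |

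The mismatch is confined to 21 and 22.

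**Step 3: how often.** P(21 or 22) = R(21, p) − R(23, p).

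| True ORR | R(21) | R(23) | P(21 or 22) |
|---|---|---|---|
| 35% | 0.0458 | 0.0126 | 3.3% |
| 40% | 0.1560 | 0.0610 | 9.5% |
| 45% | 0.3571 | 0.1900 | 16.7% |
| 50% | 0.5995 | 0.4108 | 18.9% |
| 55% | 0.8001 | 0.6618 | 13.8% |

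At the design alternative, 100% − 13.8% = 86.2% of trials show no mismatch. The R(23) column also shows what judging by the interval would mean: alpha 1.3% and power 66.2%. The plan does not adopt that rule.

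**Step 4: where it comes from.** Mainly from the level. A 95% interval that respects the two stages (stage-wise ordering) still starts at 33.1% at 21 and 34.99% at 22. The two-stage structure matters as well at 21: an ordinary 90% Clopper-Pearson interval starts at 34.6%, because the single-stage tail P(X ≥ 21 | 44, 0.35) is 0.0556, whereas the two-stage tail is 0.0458.

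**Step 5: is the planned interval sound as an estimate?** The ordinary 95% interval was computed on 14 patients after an early stop and on 44 otherwise, and its coverage was enumerated over the two-stage outcomes. The minimum is 94.4% for true ORR between 20% and 80%. Ignoring the stages costs at most about 0.6 percentage points (95.0 − 94.4).

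**Step 6: would an interval matched to the test be better?** The stage-wise two-sided 90% interval has lower limits of 33.4% at 20, 35.3% at 21 and 37.3% at 22, so it agrees with the rule at these counts. Its upper limit solves 1 − R(s + 1, p) = 0.05. P(X1 ≤ 5) is contained in that left-hand side at every stage-2 total, so the upper limit barely moves at low counts: 61.0% for every total from 6 to 16. At 10/44 (22.7%) the interval is 21.0% to 61.0%; at 14/44 (31.8%) it is 24.2% to 61.0%. In clearly failed trials it would not exclude the 55% target.

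**The case for a change.** The strongest case for acting is that this touches the primary endpoint, can be foreseen, and is cheap to settle. About 17% of successful trials at a true ORR of 55% (0.1383 / 0.8001), and about 31% at 50% (0.1887 / 0.5995), would carry an interval that includes the null value. A sentence written in advance would stop any explanation from looking post hoc, and a companion interval tied to the test would remove the mismatch for one short program and no extra patients.

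The arithmetic stands, and so does the observation that the plan is silent on sidedness and on the exact method. What does not stand is that the silence leaves anything undecided. The hypotheses point one way, rejection occurs only for high counts, and the rule is expressed in counts with no reference to the interval. A one-sided 5% test and a two-sided 95% interval answer different questions and need not agree near the boundary. The 95% level also fits the DCR interval and Appendix A.

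The companion interval is the only part with substance, and Step 6 shows that it trades one confusing display for another. If a quantity tied to the test is wanted in the report, the two-stage one-sided p-value (0.0458 at 21, 0.0251 at 22) or the one-sided 95% stage-wise lower bound (35.3% and 37.3%) gives it without the uninformative upper limit. An analyst can report either without amending the plan.

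**Conclusion.** The mismatch is real and confined to two counts, 21 and 22 of 44, with probability 13.8% at a true ORR of 55% and at most 18.9% among the values examined. It needs no change. Followed as written, the plan gives a valid decision (type I error 0.0458, power 0.8001) and an interval whose coverage never falls below 94.4% for true rates from 20% to 80%. Writing one-sided, naming Clopper-Pearson, or noting that the interval is descriptive would be courteous detail that alters no number and no conclusion.

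The figures assume the usual two-sided Clopper-Pearson reading. If the interval were a one-sided 95% bound, only 21 would conflict (34.6%), since 22 gives 36.8%. They also assume exactly 44 analysed patients. Section 9.3 says "The mITT is the analysis population for the efficacy analysis" and requires a post-baseline scan for that population, so the denominator could be smaller. That is a separate question and adds nothing to this one.

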9.4.3 ANALYSIS OF THE SECONDARY ENDPOINT(S)

The secondary efficacy endpoints (DCR, PFS and OS) will be summarized descriptively using the mITT population.

DCR

DCR is defined as the proportion of patients with RECIST disease control (CR, PR, or SD). All patients that do not meet the criteria for an objective response by the analysis cutoff date will be considered non-responders. A binomial proportion with 95% exact confidence interval will be reported.

PFS

PFS will be defined as the time from treatment initiation to the date of first documentation of disease progression or death due to any cause in the absence of documented progression. For patients who discontinue study treatment due to reasons other than progression or death, the patient will be censored at their last radiographic assessment for progression. Cumulative PFS will be descriptively summarized over time with the method of Kaplan-Meier.

OS

OS will be defined as the time from treatment initiation to the date of death due to any cause. Cumulative OS will be descriptively summarized over time with the method of Kaplan-Meier.

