with treatment naïve advanced melanoma. To evaluate the disease control rate (DCR) with the combination of cabozantinib and pembrolizumab in subjects with treatment naïve advanced melanoma. To evaluate the progression-free survival from the combination of cabozantinib and pembrolizumab in subjects with treatment naïve advanced melanoma. To evaluate the overall survival with the combination cabozantinib and pembrolizumab in subjects with treatment naïve advanced melanoma.	response (PR) per RECIST v1.1 criteria. Time to response per RECIST v1.1 criteria. DCR defined as the percentage of patients achieving CR + PR + SD at any time during the study following initiation of therapy. Radiologic progression-free survival (PFS) per RECIST v1.1 criteria. PFS is defined as the time between the first dose of study therapy and the earliest date of progression or death. Subjects who have neither progressed nor died will be censored at the last tumor assessment date for PFS. Overall survival defined as the time between the first dose of study therapy and death (subjects who have not died will be censored at the most recent last-known-alive date).	
Tertiary/Exploratory		
Biomarker evaluation: To assess changes in tumor biomarkers.	Blood samples and biopsy samples will be collected to evaluate for biomarkers and changes in tumor microenvironment.	

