8 STUDY ASSESSMENTS AND PROCEDURES

8.1 EFFICACY ASSESSMENTS

The intention of the study design is to closely monitor patients with safety follow-up and disease assessments in the absence of disease progression or other study discontinuation criteria.

For the purposes of this study, patients should be re-evaluated after the first 12 weeks of treatment and then every 12 weeks. **In addition to a baseline scan, confirmatory scans will** also be obtained at least 4 weeks and no more than 14 weeks following initial documentation of partial or complete response.

Primary efficacy endpoint is best ORR defined as the proportion of all treated subjects whose best response at any time during the study following initiation of therapy is confirmed CR or confirmed PR. This will be assessed according to the RECIST v1.1.(Appendix A).

PFS, defined as the time between the first dose of study therapy and the earliest date of progression or death. Subjects who have neither progressed nor died will be censored at the last tumor assessment date for PFS. The endpoint ORR and PFS will be assessed according to the RECIST v 1.1 criteria.

Additional efficacy endpoints will include the disease control rate (DCR) defined as the percentage of patients achieving CR + PR + SD at any time during the study following initiation of therapy. This will be assessed according to RECIST v1.1 criteria. The duration of response (DOR), is defined as the time between the date that the criteria are first met for CR or PR or SD and the earliest date of progression or death.

OS, defined as the time between the first dose of study therapy and death (subjects who have not died will be censored at the most recent last-known-alive date), will also be analyzed.

The tumor assessment (TA) performed during screening will be used as a baseline for efficacy assessments. CT/MRI imaging of the chest and abdomen is required at Screening and at each TA, regardless of the location of known metastases. In addition, CT/MRI scans must be obtained of anatomic regions not covered by the chest and abdomen scans in subjects where there is clinical suspicion of deep soft tissue metastases (eg, lesions in the thigh). Such additional CT/MRIs will be required at Screening when deep soft tissue disease is known/suspected and must be consistently repeated at all TAs if a deep soft tissue lesion is identified during Screening.

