- The main goal of confirmation of objective response is to avoid overestimating the response rate observed. In cases where confirmation of response is not feasible, it should be made clear when reporting the outcome of such studies that the responses are not confirmed.
- To be assigned a status of PR or CR, changes in tumor measurements must be confirmed by repeat assessments that should be performed no less than 4 weeks after the criteria for response are first met. Longer intervals as determined by the study protocol may also be appropriate.
- In the case of SD, follow-up measurements must have met the SD criteria at least once after study entry at a minimum interval (in general, not less than 6-8 weeks) that is defined in the study protocol

Duration of overall response

- The duration of overall response is measured from the time measurement criteria are met for CR or PR (whichever status is recorded first) until the first date that recurrence or PD is objectively documented, taking as reference for PD the smallest measurements recorded since the treatment started.

Duration of stable disease

- SD is measured from the start of the treatment until the criteria for disease progression are met, taking as reference the smallest measurements recorded since the treatment started.
- The clinical relevance of the duration of SD varies for different tumor types and grades. Therefore, it is highly recommended that the protocol specify the minimal time interval required between two measurements for determination of SD. This time interval should take into account the expected clinical benefit that such a status may bring to the population under study.

Response review

- For trials where the response rate is the primary endpoint it is strongly recommended that all responses be reviewed by an expert(s) independent of the study at the study's completion. Simultaneous review of the patients' files and radiological images is the best approach.

Reporting of results

- All patients included in the study must be assessed for response to treatment, even if there are major protocol treatment deviations or if they are ineligible. Each patient will be assigned one of the following categories: 1) complete response, 2) partial response, 3) stable disease, 4) progressive disease, 5) early death from malignant disease, 6) early death from toxicity, 7) early death because of other cause, or 9) unknown (not assessable, insufficient data).

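### The DCR paragraph of section 9.4.3 reuses the ORR scoring sentence, so read literally stable disease counts as failure; separately, no minimum interval for stable disease is set

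*Combined protocol and SAP*

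**What the plan says.** **Scoring rule.** Section 9.4.3 opens its DCR paragraph with "DCR is defined as the proportion of patients with RECIST disease control (CR, PR, or SD" and closes the bracket there. The next sentence is "All patients that do not meet the criteria for an objective response by the analysis cutoff date will be considered non-responders". The same sentence appears in 9.4.2, where it follows the definition of ORR and where response is limited to CR and PR. Nothing else in 9.4.3 says how a patient without disease control is to be scored.

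**Timing of SD.** Section 3 has "DCR defined as the percentage of patients achieving CR + PR + SD at any time during the study following initiation of therapy", and section 8.1 repeats the definition ("percentage of patients achieving CR + PR + SD at any time during the study following initiation of therapy"), adding that it is assessed by RECIST v1.1. Appendix A, under Confirmation, says of SD that "follow-up measurements must have met the SD criteria at least once after study entry at a minimum interval". It describes that interval as generally at least 6-8 weeks and to be set by the protocol. Under Duration of stable disease it adds that "it is highly recommended that the protocol specify the minimal time interval required between two measurements for determination of SD". No section of the protocol gives a value.

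**When scans happen.** The first scheduled scan is at week 12. The study calendar also marks tumor imaging at the end-of-treatment visit, which falls 30 days (+/- 7) after the last dose, or before another treatment starts if that is sooner. Section 8.1 allows extra scans when progression is suspected. The mITT population in 9.3 needs one post-baseline image and places no condition on its timing.

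**The concern.** DCR is a named phase 2 secondary endpoint. Two consecutive sentences in 9.4.3 put an SD patient in the numerator and then take the patient out. A programmer who codes the scoring sentence as written would report a DCR identical to ORR, and the endpoint would carry no information of its own.

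The missing interval matters in a smaller way. SD is the residual RECIST category (neither PR nor PD), and without a minimum interval one very early scan can supply it. That same scan admits the patient to the mITT population. Under the definitions in sections 3 and 8.1, the SD would still count if the week 12 scan showed progression. Section 8.1 also starts its duration clock when CR, PR or SD is first met, so the choice of who counts as SD carries into the duration measure.

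**Working it through.** **1. The plan's own figure.** The documents give no target for DCR. The only design figure is for ORR (9.2, 9.4.2): stop if 5 or fewer of 14 respond, reject the null with at least 21 of 44, rates 35% and 55%. With b for the binomial probability,

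P(reject | p) = sum over x = 6 to 14 of b(x; 14, p) × P[Bin(30, p) ≥ 21 − x].

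This gives 0.0458 at p = 0.35 and 0.8001 at p = 0.55, so the stated alpha of 0.05 and power of 80% reproduce. DCR does not enter this calculation.

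**2. What the scoring sentence does.** Let R be the number with CR or PR, S the number with SD as best response, and N the number analysed.

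- By the definition in 9.4.3: DCR = (R + S)/N.
- By the scoring sentence read literally: DCR = R/N = ORR.
- Difference: S/N, the whole SD fraction.

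Illustration with N = 44 and R = 21, the smallest count that rejects the null. The values of S are assumed, since the documents give no expected SD rate for the combination. Intervals are exact 95%.

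| S (assumed) | Literal rule | Counting SD | Difference |
|---|---|---|---|
| 4 | 21/44 = 47.7% (32.5-63.3) | 25/44 = 56.8% (41.0-71.7) | 4/44 = 9.1 points |
| 9 | 47.7% | 30/44 = 68.2% (52.4-81.4) | 9/44 = 20.5 points |
| 17 | 47.7% | 38/44 = 86.4% (72.6-94.8) | 17/44 = 38.6 points |

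**3. How early an SD scan can be.** If the last dose falls d days after the first, the end-of-treatment scan falls d + 23 to d + 37 days after the first, unless a new treatment brings it forward.

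- d = 0: 23-37 days, or 3.3-5.3 weeks. This is below 6 weeks.
- d = 14: 37-51 days, or 5.3-7.3 weeks. This straddles 6 weeks.
- d = 28: 51-65 days, or 7.3-9.3 weeks. This is past 6 weeks and straddles 8.

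At the early edge of the window, the scan precedes 6 weeks (42 days) only if d < 42 − 23 = 19. It precedes 8 weeks (56 days) only if d < 56 − 23 = 33. Scheduled scans, which begin at week 12, are not exposed.

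**4. Size of the second point.** Each patient whose SD rests only on such a scan adds 1/44 = 2.3 points. Starting from 30/44 = 68.2%, moving 1, 2 or 4 such patients (assumed) to no disease control gives 29/44 = 65.9%, 28/44 = 63.6% or 26/44 = 59.1%.

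**The case against.** The strongest reply is that the scoring sentence is an obvious carry-over. Three definitions (sections 3, 8.1 and 9.4.3) include SD, and the sentence only labels patients as non-responders without explicitly removing SD from the numerator. A sensible analyst would follow the definitions. That makes the intent clear and the repair easy. It does not make the text correct: this is the only scoring rule in the paragraph, and it contradicts the line above it.

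On the interval, it can be said that section 8.1 places DCR under RECIST v1.1, and that Appendix A already asks for a minimum interval "at a minimum interval (in general, not less than 6-8 weeks) that is defined in the study protocol". This limits the problem but does not close it, because Appendix A hands the value to the protocol and the protocol leaves it out. It is also fair that few patients are exposed: an early scan requires very early discontinuation, an early switch of therapy or an unscheduled scan. Section 7.2 keeps patients who stop for reasons other than progression, and who still consent to follow-up, on scheduled scans until progression, so many would also have a week 12 image.

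Three stronger readings do not hold.

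- A reader might infer that DCR is biased in both directions at once. The two points are alternative readings from different sections: under the literal 9.4.3 sentence no SD counts, and under sections 3 and 8.1 any SD counts. They cannot act together.
- A reader might take the cabozantinib melanoma trial in the background (ORR 5%, SD 39%) and conclude that DCR here would be 5% in place of 44%. That trial was monotherapy at 100 mg in a cohort 30% uveal and 8% mucosal, both excluded here, so it does not size the effect for the combination.
- A reader might conclude that DCR will rise with early intolerance. The documents give no rate of early discontinuation and no early SD rate.

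**Conclusion.** The scoring sentence in 9.4.3 is wrong as written. Applied literally it makes DCR equal to ORR and understates it by the full SD fraction: 9.1 to 38.6 points for 4 to 17 SD patients among 44, where those counts are assumptions. The missing SD interval is a real but narrower gap, confined to end-of-treatment and unscheduled scans before week 12. It is worth 2.3 points per affected patient if all 44 are in the mITT population; how many would be affected cannot be derived from the documents.

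Both should be corrected before DCR is computed. Neither touches the primary conclusion: section 9.1 sets no hypotheses for secondary endpoints and 9.4.3 summarises DCR descriptively, so the ORR rule, N = 44 and the power stand.

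**What to change.** In the DCR paragraph of 9.4.3, replace the scoring sentence with: *Patients whose best overall response is not CR, PR or SD by the analysis cutoff date will be counted as not having disease control.*

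In sections 3, 8.1 and 9.4.3, state one minimum interval from first dose for SD, consistent with Appendix A, and say that SD seen only before it counts as no disease control. Appendix A's general guide of 6-8 weeks is enough to close the gap. Anchoring at the first scheduled scan in week 12 is possible but stricter, since it would reject SD documented at, say, week 9 or 10. That choice is the sponsor's.

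The cost is wording in three sections. No new scans or data are needed. The reported DCR may be slightly lower than if SD were credited whenever seen.
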